7.1.3 Follow-Up Phase

Patients will be followed for safety monitoring (30 + 4 days) after their final study drug infusion and will have an End of Study visit by telephone at the following times: either (1) at completion of the Extension Phase or (2) at early termination if the patient voluntarily withdraws consent. Patients who terminate the study prematurely will continue to be followed by having all Early Termination assessments performed. Patients who terminate the study prematurely who are unable to be on-site for the Early Termination visit will be contacted by telephone for safety follow-up.

If withdrawn from study drug, regardless of reason, the patient will continue study visits to the end of Treatment Period 12.

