7.6.3.2 Phase 2 Studies with SEL-212

7.6.3.2.1 Phase 2 Study SEL-212/201

The Phase 2 study SEL-212/201 was designed as an open-label, ascending multiple-dose study of the combination drug, SEL-212, combined with an open-label, multiple-dose evaluation of SEL-037 (pegadricase) alone in patients with symptomatic gout and elevated blood uric acid. Part A of the study consisted of three 28-day treatment cycles of SEL-212, which was then followed by Part B, which consisted of two 28-day treatment cycles of SEL-037 alone, with a primary objective of assessing the safety, tolerability, PK, PD of SEL-212 (i.e., the combination of SEL-110 and SEL-037). Additional assessments include the ability of SEL-212 to reduce serum uric acid levels and prevent anti-drug antibodies to uricase and pegadricase. Part C of the study consisted of 5 monthly doses of SEL-212.

In Study SEL-212/201 with SEL-212, sUA levels remained consistently below 6 mg/dL in 70% to 89% of evaluable Part A patients administered SEL-212 once monthly for 3 months. The control of sUA occurred in the context of low incidences of infusion reactions, anaphylaxis, and gout flares as well as treatment-emergent adverse events (TEAEs) known to be potentially associated with rapamycin (sirolimus – Rapamune®). Data support a once monthly dosing regimen. For cohorts 7-12 with SEL-110 doses of 0.1 mg/kg or higher, 46% of evaluable patients had sUA <6 mg/dL at week 20.

In Part C cohorts receiving 5 monthly doses of SEL-212, 61%, 71%, and 67% of eligible patients in Cohorts 13, 15, and 17, respectively, maintained sUA control (sUA, <6 mg/dL) at week 12 without the development of ADAs. All 21 patients in cohorts 13, 15 and 17 who had sUA < 6 mg/dL at week 12, maintained sUA control through the end of treatment period 5 and had sUA < 6 mg/dL at week 20.

The efficacy signal of SEL-212 in SEL-212/201 persists across multiple treatment cycles in all cohorts and through all 5 treatment cycles when SEL-212 is given at each treatment, as demonstrated by dose-dependent reductions in sUA levels below 6 mg/dL and ADA suppression in conjunction with increasing SEL-110 dose levels up to 0.15 mg/kg.

Cohorts 7, 11, 13 and 17 represent the dose regimens that will be evaluated in the Phase 3 program (0.1 or 0.15 mg/kg SEL-110 and 0.2 mg/kg SEL-037). Part C cohorts 13, 15, and 17 received 5 once monthly doses of SEL-212, and patients in the proposed Phase 3 program will receive a total of 6 or 12 once monthly doses of SEL-212.

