3. Treatment Period 6 only. Treatment Period 6 Day 28 assessment will be used for Treatment Period 7 Day 0 pre-dose assessment. Do not repeat sample collection on Treatment Period 7 Day 0.
4. Premedication to minimize potential infusion reactions: oral antihistamines at 12 (± 2) hours and 2 (± 1) hours and IV steroids at 1 (± 0.5) hours prior to study drug.
5. Obtain sample prior to study drug infusion.
6. Obtain sample 1 hour (+15/-0 min) after completion of infusion of Component 2. If a patient is withdrawn from study drug, the post-dose uricase activity and post-dose sUA samples do not need to be collected.
7. Component 1 will be SEL-110.36 at 0.1 mg/kg for patients randomized to treatment with SEL-212A and SEL-110.36 at 0.15 mg/kg for patients randomized to SEL-212B or will be placebo for patients randomized to placebo.
8. Before starting infusion with Component 2, a period of up to approximately 30 minutes is permitted after completion of infusion of Component 1.
9. Component 2 will be SEL-037 for patients randomized to treatment with either SEL-212A or to SEL-212B or will be placebo for patients randomized to placebo.

PHASE 3 STUDY: SEL-212/301
VERSION: 6.1

EFFECTIVE DATE

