#### **4.3. Exploratory Endpoints for the Double-blind Treatment Phase**

- Levels of uricase activity in patients receiving SEL-212
- Levels of monosodium urate crystal deposits and/or total body monosodium urate crystal deposits (imaging patients only)
- Levels of inflammatory and tolerogenic biomarkers
- Changes in antibody production (anti-uricase and anti-pegadricase) in patients in the SEL-212 groups
- Gout flare incidence during Treatment Periods 4-6
- Gout flare incidence during Treatment Periods 1-3 based on self-reported weekly gout flare diary
- Gout flare incidence during Treatment Periods 1-6 based on self-reported weekly gout flare diary
- Gout flare incidence in the Treatment Periods 4-6 based on self-reported weekly gout flare diary
- Assessment of association between multiomic markers of gout and treatment effect in patients treated with SEL-212
- Immune tolerance related multiomic markers in patients on SEL-212 who developed anti-uricase and anti-pegadricase antibodies vs. those patients on SEL-212 that did not develop anti-uricase and anti-pegadricase antibodies

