### **5.3. Intent-to-Treat Set**

The Intent-to-Treat (ITT) Set will include all randomized patients who were dosed. Patients will be analyzed according to randomized treatment group assignment. Replaced subjects will not be included in the ITT. The ITT will be used as primary population for analyses of efficacy endpoints.

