### **9.3.3. Additional Secondary Efficacy Endpoints and Analyses**

- Percentage of patients who achieve and maintain reduction of sUA < 6 mg/dL for 100% of the time during TP6:

A frequency table of number and percentage of patients who achieve and maintain reduction of sUA < 6 mg/dL for 100% of the time during TP6 will be provided on the ITT population. Each SEL-212 treatment group will be compared versus placebo using the MH estimate and test for common risk difference considering the randomization stratum of tophus presence (yes/no) on the ITT population. In addition, 95% confidence intervals for treatment differences between each SEL-212 treatment group and placebo will be computed.

- Number with pre-dose sUA values < 6 mg/dL during TPs 2-6 for each patient:

A summary table of the mean number of TPs with pre-dose sUA values < 6 mg/dL during TP2 to TP6 will be provided by treatment group on the ITT population. Each SEL-212 treatment group will be compared versus placebo using ANCOVA model with the number of pre-dose values < 6 mg/dL during TPs 2-6 for each patient as dependent variable and treatment group as independent fixed effect variable. 95% confidence intervals for treatment differences between each SEL-212 treatment group and placebo will be presented.

- Anti-pegadricase and anti-uricase antibody formation and levels, pre-treatment for each treatment period in the SEL-212 active treatment arms during Treatment Periods 1-6:

Summary table of pre-treatment values of each variable will be provided by treatment period and by SEL-212 treatment group on the ITT population.

A descriptive summary table of D21 anti-pegadricase and anti-uricase antibody titers, D21 uricase activity values and D21 SUA values at each treatment period, stratified by treatment arm and whether or not the D21 SUA was above or less than or equal to the stopping rule level for that TP (i.e.  $\leq 1$  mg/dL in TP1 and  $\leq 6$  mg/dL in TPs 2-6).

This document is confidential.

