#### **9.3.4. Exploratory Endpoints**

All exploratory endpoints will be summarized on the ITT population.

- Levels of uricase activity in patients receiving SEL-212:

Summaries for each SEL-212 treatment group will be provided by period.

- Effect on monosodium urate crystal deposits and/or total body monosodium urate crystal deposits (imaging patients only):

Frequencies and summaries will be provided by treatment group, and period, if appropriate.

- Levels of inflammatory and tolerogenic biomarkers:

Frequencies and summaries will be provided by treatment group, and period, if appropriate..

- Changes in antibody production (anti-uricase and anti-pegadricase) in patients in the SEL-212 groups:

Summaries for each SEL-212 treatment group will be provided by period.

- Gout flare incidence during Treatment Periods 4-6

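### From Treatment Period 2 on, the Day 21 antibody/uricase-activity/sUA table and the by-period activity and antibody summaries pool patients dosed in the period with patients already off SEL-212

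*SAP*

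**What the plan says.** **Follow-up after withdrawal.** Protocol 7.1.3 states: "If withdrawn from study drug, regardless of reason, the patient will continue study visits to the end of Treatment Period 12". The only sampling relief is in Protocol Appendix B, footnote 6 (repeated in SAP Table B): "If a patient is withdrawn from study drug, the post-dose uricase activity and post-dose sUA samples do not need to be collected". Pre-dose and Day 21 draws for antibodies, activity and sUA stay on the schedule.

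**Tables.**
- SAP 9.3.3, pre-treatment antibodies: "Summary table of pre-treatment values of each variable will be provided by treatment period and by SEL-212 treatment group on the ITT population".
- SAP 9.3.3, Day 21 titers, activity and sUA in TP1-6: "stratified by treatment arm and whether or not the D21 SUA was above or less than or equal to the stopping rule level". No analysis set is named.
- SAP 9.3.4, which includes uricase activity and antibody change by period: "All exploratory endpoints will be summarized on the ITT population". SAP 5.3 defines that set: "The Intent-to-Treat (ITT) Set will include all randomized patients who were dosed". One dose is enough to be counted in every later period.
- SAP 9.3.5 summarises activity over TP1-12, and antibodies by period, on the Extension Phase Evaluable Set. Under Protocol 7.1.4, patients who met the stopping rule go on attending in the extension without drug.

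**Stopping rule (Protocol 7.4.1.1).** Two conditions must both hold: sUA below 2.0 mg/dL one hour after the TP1 infusion, and Day 21 sUA above 1.0 mg/dL in TP1 or above 6.0 mg/dL in TP2-11.

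**The concern.** The variable that splits the Day 21 table is the second condition of the rule that takes patients off drug. Once a patient is stopped, later Day 21 values come from a period with no enzyme given. Activity is then low and sUA tends to be high whatever the titer. From TP2 on, the above-level group mixes two kinds of patient: those who lost control while dosed, who are informative about antibodies and enzyme activity, and those who received nothing.

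Protocol 7.6.6 intends antibodies to be related to response to SEL-212, and this table is where a reader would look. Pooling obscures the association between titer and retained activity. It also makes mean activity by period fall, and differ between the two doses, partly because of how many patients have been withdrawn.

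**Working it through.** **Plan figure reproduced.** The documents give no figure for the dosed/undosed mix. The stated figure that supplies the 45% response rate is the sample size. With 45% v 5%, two-sided alpha 2.5%, power 90% and continuity correction, I obtain 32 per arm, as stated (27 without the correction); 32/0.92 = 34.8, rounded up to 35. The planned arm size is 40.

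**Inputs for the loss paths.** 45% assumed response at TP6 (SAP 3.5). Phase 2 control at week 12 of 61%, 71% and 67% in three cohorts, after which all 21 controlled patients "maintained sUA control through the end of treatment period 5 and had sUA < 6 mg/dL at week 20" (Protocol 7.6.3.2.1).

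**Model.** Let S(k) be the fraction of an active arm still dosed and controlled at Day 21 of TPk, with S(0) = 1. Assume everyone who loses control is withdrawn and still sampled.
- Undosed share of the above-level group in TPk = (1 − S(k−1)) / (1 − S(k))
- Patients newly above the level who were dosed in TPk = 40 × (S(k−1) − S(k))

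Example, constant hazard to 45%: S(3) = 0.45^(3/6) = 0.671 and S(4) = 0.45^(4/6) = 0.587. In TP4 there are 40 × 0.329 = 13.2 undosed and 40 × 0.084, about 3.3, newly failing on drug; the undosed share is 0.329/0.413 = 80%.

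| Assumed path | TP2 | TP3 | TP4 | TP5 | TP6 |
|---|---|---|---|---|---|
| Constant hazard to 45% | 53% | 71% | 80% | 85% | 88% |
| Linear to 45% | 50% | 67% | 75% | 80% | 83% |
| Half of losses in TP1, then constant hazard to 45% | 81% | 85% | 88% | 90% | 92% |
| 71% at TP3, 45% at TP6 | 53% | 70% | 74% | 82% | 87% |
| 61% at TP3, 45% at TP6 | 54% | 72% | 87% | 89% | 91% |
| 71% at TP3, no later loss | 53% | 70% | 100% | 100% | 100% |
| 61% at TP3, no later loss | 54% | 72% | 100% | 100% | 100% |
| 45% at TP3, no later loss | 57% | 75% | 100% | 100% | 100% |

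In TP1 the share is 0% on every path, because everyone in the ITT set was dosed.

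**Sensitivity 1.** Suppose 5% of the arm stays dosed above the level because the one-hour condition was not met. The denominator becomes 1 − S(k) + 0.05. In the example, TP4 is 0.329/0.463 = 71%. Over all paths, TP4-6 is 66-92%.

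**Sensitivity 2.** Suppose 25% of undosed patients are at or below 6 mg/dL, for instance on urate-lowering therapy (ULT). Over all paths, TP4-6 is 69-100%, and undosed patients make up 9-23% of the at-or-below group.

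**Timing.** The first undosed Day 21 falls 28 + 21 = 49 days after the last dose at nominal timing. The visit windows allow 24 + 20 = 44. The first Day 21 beyond 60 days is nominally the second undosed one, at 56 + 21 = 77 days.

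**On-drug cell sizes.** Patients newly above the level while dosed, per arm of 40: about 4-11 in TP1, 3-7 in TP2, 2-6 in TP3 and 0-4 in each of TP4, TP5 and TP6.

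**The case against.** The tables are descriptive. Uricase activity is exploratory, and the Day 21 table sits under an additional secondary endpoint. SAP 10.1 counts patients meeting the stopping rule by arm and period, and SAP 8.1 plots discontinuation by period, so readers can see how many are off drug. The time-to-antibody endpoints describe immunogenicity separately. All of this stands and limits the importance of the point. It does not remove it, because those counts do not show which titers and activity values in a given cell came from dosed patients.

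Three stronger readings are tempting and not supported:
- *The above-level group in TP4-6 is almost entirely undosed.* That follows only if the Phase 2 pattern (no loss among 21 patients) repeats. Paths that keep losing patients down to 45% leave about 8-26% dosed, and more if some stay dosed because the one-hour condition was not met. Nor is 45% response an on-drug rate: the estimand behind it also counted consent withdrawal and loss to follow-up as failures, and such patients give no later samples. The 71% comes from cohort 15, which the protocol does not list among the Phase 3 regimens.
- *The tables cannot show whether antibodies cause loss of activity.* TP1 is wholly on drug, and TP2-3 still contain on-drug failures. No descriptive table would show cause in any case.
- *The ITT summary contradicts the endpoint wording.* "Levels of uricase activity in patients receiving SEL-212" can be read simply as the active arms, which is how SAP 9.3.4 implements it.

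Restricting the tables to dosed patients alone would also be a poor remedy. It selects patients who survived a rule driven by sUA, and it nearly empties the TP4-6 above-level cells.

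**Conclusion.** The point holds as a matter of presentation and interpretability. From TP2 on, the plan pools dosed and undosed SEL-212 patients in the Day 21 table and in the by-period activity and antibody summaries, through TP12 for the latter. Undosed patients are the majority of the above-level group in TP4-6 on every path tested, at about 66-100%. That range rests on assumed loss paths, on withdrawn patients continuing to give samples, and on the two sensitivities taken one at a time. The trial's actual stopping pattern will decide the figure.

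The at-or-below group may be affected too. Protocol 7.4.1.1 allows return to ULT 60 days after the last dose, at the investigator's discretion, while Protocol 10.5 has patients stay off it throughout participation. If ULT is used, some undosed patients could appear controlled with no enzyme present.

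The primary analysis, the key secondary tests, alpha and power are untouched.

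**What to change.** 1. In SAP 9.3.3, name the analysis set for the Day 21 table.
2. Show the Day 21 table (TP1-6) and the by-period activity and antibody summaries in SAP 9.3.3, 9.3.4 and 9.3.5 (TP1-12) in two rows, study drug given or not given in that period. Give time since last dose for the undosed row, and keep both rows visible.
3. Add one table of titer, activity and sUA at each patient's first Day 21 value above the stopping level, by SEL-212 arm. Flag patients who were already off drug for another reason at that visit.
4. Footnote the later on-drug rows: they describe patients selected by the stopping rule and are not randomized dose comparisons.
5. Reconcile Protocol 7.4.1.1 and 10.5 on ULT after withdrawal, and mark ULT use in the undosed rows.

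**Cost.** SAP wording and one dosing flag per patient and period, from records already collected. No samples are added and no data are dropped. The on-drug above-level cells will be sparse in TP4-6, at about 0-4 patients per arm. That is the number actually informative there, and the first-failure table is meant to make up for it.

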## Statistical Analysis Plan

Sponsor: Selecta Biosciences

Protocol No.: SEL-212/301

---

- In patients with tophi at Baseline, the percentage of patients with at least PR (as best response) in overall tophus response evaluation until Day 0 of Treatment Period TP4

Pairwise comparison of each SEL-212 treatment group versus placebo will be performed using the Chi-square test with continuity correction. In addition, 95% confidence intervals for treatment differences between each SEL-212 treatment group and placebo will be computed.

Frequency table of tophaceous patients at baseline with best response in the overall tophus evaluation resulting in at least PR / stable disease progressive disease will be provided by treatment group and period on the ITT population.

The time until the first tophus reduction (i.e. the first time PR (as best response) is assessed in overall tophus response) will be summarized using descriptive statistics by treatment group for tophaceous patients at baseline in the ITT population.

- Percentage of patients with development of new tophi in the subgroups of tophaceous patients and in non tophaceous patients at baseline during Treatment Periods 1-6:

A frequency table of number and percentage of patients will be provided by treatment group and tophus status at baseline on the ITT population who developed new tophi during the study until Day 28 of TP6, i.e. were classified as PD due to new tophi in the overall tophus response evaluation. Pairwise comparison of each SEL-212 treatment group versus placebo will be performed using the Chi-square test with continuity correction. In addition, 95% confidence intervals for treatment differences between each SEL-212 treatment group and placebo will be computed. The actual value and the change from baseline of the total number of tophi will be summarized for each scheduled visit by treatment group. Location of tophus, palpation and appearance will be summarized by category, as appropriate, by treatment group for each scheduled visit.

- Change from baseline to Day 28 of TP6 in subscales of Health Assessment Questionnaire (HAQ-DI), in subscales of Short Form Health Survey (SF-36) and in Provider Global Assessment of Disease Activity (PGA)

Summary table of actual values and change from baseline will be provided for all subscales of HAQ-DI, for all subscales of SF-36, the two component scores of SF-36, and the PGA, by period and treatment group. Pairwise comparison of each SEL-212 treatment group versus placebo will be performed using MMRM with the change from baseline in the respective health assessment score as dependent variable and treatment, period, treatment by period interaction, randomization stratum, and baseline value of the respective health assessment as fixed effects. The LSMean difference between each SEL-212 and placebo treatments groups will be presented for TP6, along with its 95% confidence interval, and 2-sided p-values.

HAQ-DI subscales and SF-36 subscales and component scores are described in Sections [9.3.2.7](#) and [9.3.2.3](#) of this SAP, respectively. The PGA will be administered to assess the severity of the patient's disease on a scale from 0 (patient feels "very well") to 100 (patient feels "very poor"). Lower scores indicate less severe disease.

- Percentage of Patients with Gout Flares:

Frequency table of the number and percentage of patients reporting at least one gout flare in the study until end of Month 6, in the first 3 months, and the next 3 months will be summarized by treatment group on the ITT population.

This document is confidential.

The number and percentage of patients with at least one life-threatening / at least one severe but no life-threatening / at least one moderate but no severe or life-threatening / only mild gout flares will be presented for each treatment group for all 6 months, but also per 3-month period (first 3 months and next 3 months) on the ITT population.

The percentage of patients with gout flares will be compared between each SEL-212 treatment group versus placebo on the ITT population using the MH estimate and test for common risk difference considering the randomization stratum of tophus presence (yes/no). This analysis will be performed separately for the whole treatment period of 6 months and for the first 3 months after start of study treatment. 95% confidence intervals for treatment differences in proportions between each SEL-212 treatment group and placebo will be computed.

- Change from Baseline to Day 28 of TP6 in number of swollen joints:

The number of swollen joints at scheduled visits and the change from baseline will be summarized by treatment group on the ITT population. Pairwise comparison of each SEL-212 treatment group versus placebo will be performed using MMRM with the change from baseline in the number of swollen joints as dependent variable and treatment, period, treatment by period interaction, randomization stratum, and baseline number of swollen joints as fixed effects. The LSMean difference between each SEL-212 and placebo treatment groups will be presented for TP6, along with its 95% confidence interval, and 2-sided p-values.

- Length of time patients are anti-uricase antibody free or before induction of anti-uricase antibody levels above baseline in patients receiving SEL-212:

A summary table will be provided for each SEL-212 treatment group on the ITT population.

- Length of time patients are anti-pegadricase antibody free or before induction of anti-pegadricase antibody levels above baseline in patients receiving SEL-212:

A summary table will be provided for each SEL-212 treatment group on the ITT population.

#### **9.3.4. Exploratory Endpoints**

All exploratory endpoints will be summarized on the ITT population.

- Levels of uricase activity in patients receiving SEL-212:

Summaries for each SEL-212 treatment group will be provided by period.

- Effect on monosodium urate crystal deposits and/or total body monosodium urate crystal deposits (imaging patients only):

Frequencies and summaries will be provided by treatment group, and period, if appropriate.

- Levels of inflammatory and tolerogenic biomarkers:

Frequencies and summaries will be provided by treatment group, and period, if appropriate..

- Changes in antibody production (anti-uricase and anti-pegadricase) in patients in the SEL-212 groups:

Summaries for each SEL-212 treatment group will be provided by period.

- Gout flare incidence during Treatment Periods 4-6

